### **B.8.2. Definition of Success**

The subject's self-reported pain intensity score based on the 10 cm Visual Analog Scale (VAS) is considered the outcome measure for the efficacy component of the primary endpoint. VAS is a widely used outcome measure in assessing pain. It is a reliable and valid method, which is easy to administer, and requires minimal training for the test administrator. VAS scores will be collected for both back and leg pain.

Study success will be declared if the superiority test for the primary effectiveness endpoint is statistically significant.

There are no additional pre-specified subject or study-level success criteria for secondary and tertiary endpoints.

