3.1 Randomization

Subjects meeting study entrance criteria will be randomized in a 1:1 ratio to one of two study treatment groups:

- Test treatment group with DTM™ SCS programming approach with CMM
- Control treatment group with CMM alone

Randomization will be stratified by gender and whether the subject has leg pain or no leg pain at Baseline and by study site. Randomization will be done at each study site by randomly permuted blocks. Randomization assignments will be computer-generated and allocated via the Electronic Data Capturing (EDC) system.

Statistical Analysis Plan		Page 6 of 14
Sponsor SGX International	Study EU RCT DTM SCS vs. CMM	Version 3.0

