5.6 Repeated Measures Analyses Methods

For repeated measures models based on assessing measurements over time, estimation will be based on maximum likelihood (for binary data, based on a Laplace approximation). Such methods produce validate estimates when there is missing data that is “missing at random”. A compound-symmetric covariance structure will be used to account for within-subject correlation due to repeated observations on subjects. Time will be treated as a categorical variable. Least-square means estimates will be produced to assess differences between groups at each time point and averaged over the first 6 months.

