5.7.1.1 Primary Analysis

The *primary efficacy endpoint* will be evaluated with a Pearson Chi-square binomial test for superiority at the two-sided 0.05 alpha level.

H_0 : The percentage of subjects (P) who achieve a 50% improvement in their back VAS pain score at 6 months in the Test group is the same as in the Control group.

$$P_{\text{Test}} = P_{\text{Control}}$$

H_1 : The percentage of subjects (P) who achieve a 50% improvement in their back VAS pain score at 6 months in the Test group is superior to that in the Control group.

$$P_{\text{Test}} \neq P_{\text{Control}}$$

Primary analysis will be based on the mITT analysis set.

In addition to the results from the hypothesis test, the numerator and denominator and percentage responders will be presented.

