5.7.1.2 Handling of Missing Data

For subjects in the DTM™ SCS arm who do experience an unsuccessful Trial Phase, also referred to as a **Trial Failure**, results (i.e., VAS back scores) from the Trial Phase will be utilized for the primary endpoint. Specifically, the Trial Phase results of subjects who failed the Trial Phase will be attributed for each time point throughout the study, as if they remained in the study.

Subjects who did not complete the Trial Phase due to withdrawal (e.g., an adverse event experienced during the Trial Phase, physician withdrawal due to non-compliance, withdrawal of consent, etc.), will not be included in the mITT analysis data set.

In the event of missing primary endpoint data among the mITT subjects either randomized to control or DTM™ SCS subjects who did complete the Trial Phase, the primary analysis for the primary endpoint will be conducted using multiple imputation (MI) methodology rather than the methods specified in Section 5.7.1.1. The specified Pearson Chi-square test will be presented for the observed data as a supporting analysis.

For the MI analysis each missing datum is replaced by multiple values in multiple datasets. The imputed datasets are then analyzed and combined for inference. Since the primary efficacy, and secondary efficacy endpoints, are based on the same underlying data of change in VAS, and vary only in the parameterization (continuous VAS vs. dichotomized responder) or value used for the null hypothesis, the same imputed data sets will be used for the analysis of each endpoint. Imputation will be performed separately by treatment group.

Statistical Analysis Plan		Page 10 of 14
Sponsor SGX International	Study EU RCT DTM SCS vs. CMM	Version 3.0

For each imputation model, covariates will include:

- Baseline variables: age (years), gender, number of year(s) since diagnosed with chronic back pain, unilateral versus bilateral pain, back pain VAS
- Follow-up variables: end of trial phase back pain VAS, follow-up back pain VAS (after device activation) from 1 month through 24 months. The imputation models employed will correspond to the hypothesis being tested, for the primary and secondary endpoints through 6 months, the models will use data through 6 months. For secondary endpoints post 6 months, the model will be extended to the relevant time point.

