Missing data will be imputed using the PROC MI procedure in SAS. PROC MI imputes missing covariates in the order variables are listed on the VAR statement. The variables will be listed on the VAR statement in the order listed above. Missing covariates will be imputed using fully conditional specification (FCS) methods. The regression method will be used to impute the missing endpoint values. If necessary to facilitate imputation, an augmented likelihood approach will be used. Explorations to omit predictors may be conducted if the primary effectiveness multiple imputation models will not converge.

For each multiple imputation model, 100 imputed datasets will be generated. The Pearson Chi-square statistic will be computed in each imputed dataset. The Chi-square statistics will be transformed using the Wilson-Hilferty transformation to provide an approximately normal test statistic and standard error. Additionally, the proportions of responders will be estimated for both arms in each imputation. The normalized test statistics and estimated proportions with the associated standard errors will then be combined for inference using standard methods such as those available in SAS PROC MIANALYZE or other valid statistical software.

An additional supporting analysis of the primary endpoint will use likelihood based repeated measures models to produce estimates of the primary endpoint by treatment group and the p-value for a difference between treatment groups in the presence of the missing data.

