5.7.2 Secondary Endpoints

The following secondary endpoints will be evaluated:

- If the primary efficacy endpoint in the test group is found to be superior to that in the control group, then a secondary endpoint will evaluate whether the proportion of subjects who achieve a 50% improvement in their back pain VAS score at 1, 3, 9, 12, 18 or 24 months in the test group is superior to that in the control group. A superiority test based on the difference in proportions will be performed based on the following null hypothesis, with a two-sided p-value of 0.05 or less considered evidence of statistical significance. A separate hypothesis test will be conducted for each time point.

Statistical Analysis Plan		Page 11 of 14
Sponsor	Study	Version
SGX International	EU RCT DTM SCS vs. CMM	3.0

H_0 : The proportion of subjects (P) who achieve a 50% improvement in their back pain VAS score at 1, 3, 9, 12, 18, or 24 months in the Test group is less than or equal to that in the Control group.

$$P_{\text{Test}} = P_{\text{Control}}$$

H_1 : The proportion of subjects (P) who achieve a 50% improvement in their back pain VAS score at 1, 3, 9, 12, 18, or 24 months in the Test group is greater than that in the Control group.

$$P_{\text{Test}} \neq P_{\text{Control}}$$

- Change in mean VAS will be evaluated with two-sample t-test of non-inferiority in means with a 0.65 cm non-inferiority margin at 6 months.

H_0 : The change (C) in subject's VAS pain intensity score relative to baseline at the Primary Efficacy Assessment in the Test group is worse than that of subjects in the Control group by more than 0.65 cm.

$$C_{\text{Test}} \geq C_{\text{Control}} + 0.65 \text{ cm}$$

H_1 : The change (C) in subject's VAS pain intensity score relative to baseline at the Primary Efficacy Assessment in the Test group is no more than 0.65 cm worse than the mean change from baseline in the control group.

$$C_{\text{Test}} < C_{\text{Control}} + 0.65 \text{ cm}$$

The non-inferiority margin of 0.65 cm was selected based on a previous study of a similar therapy against traditional SCSⁱ. In that study, the experimental therapy showed a 4.9 point improvement while traditional SCS showed a 3.6 point improvement for a difference of 1.3 points. Taking 50% of this treatment effect yields the margin of 0.65 cm. If the null hypothesis is successfully rejected for the non-inferiority test, a test for superiority of treatment to control will be performed based on a two-sided 0.05 alpha level.

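### Optional refinement: the 6-month VAS comparison uses baseline VAS only by subtraction and ignores gender and leg pain; a supportive ANCOVA is cheap, but its gain is small and uncertain

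*SAP*

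**What the plan says.** On allocation, SAP 3.1 states: "Randomization will be stratified by gender and whether the subject has leg pain or no leg pain at Baseline and by study site". Protocol B.6.4 names gender and leg pain and has permuted blocks at each site.

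On analysis:

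- **6-month VAS (SAP 5.7.2; Protocol B.9.2.2):** "Change in mean VAS will be evaluated with two-sample t-test of non-inferiority in means with a 0.65 cm non-inferiority margin at 6 months". If non-inferiority is shown, superiority is tested at two-sided 0.05. When data are missing, SAP 5.7.2.1 combines a plain difference in mean change across imputed datasets.
- **Responders (SAP 5.7.1.1):** the primary endpoint "will be evaluated with a Pearson Chi-square binomial test for superiority at the two-sided 0.05 alpha level". Under imputation (SAP 5.7.1.2), "The Pearson Chi-square statistic will be computed in each imputed dataset".
- **Repeated measures (SAP 5.6):** categorical time, compound symmetry and maximum likelihood are specified. "Least-square means estimates will be produced to assess differences between groups at each time point and averaged over the first 6 months". No baseline covariate is named.
- **Imputation model (SAP 5.7.1.2):** "Baseline variables: age (years), gender, number of year(s) since diagnosed with chronic back pain, unilateral versus bilateral pain, back pain VAS". Gender and baseline VAS are listed; leg pain yes/no is not.
- **Success (Protocol B.8.2):** it depends on the primary superiority test. "There are no additional pre-specified subject or study-level success criteria for secondary and tertiary endpoints".

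**The concern.** Two of the three stratification factors, and the baseline value of the outcome, are collected before randomization and then play no part as covariates in the 6-month VAS comparison. Three things follow in principle.

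- A change score fixes the slope on baseline at 1, whereas ANCOVA estimates it. If the true slope is below 1, the change score over-corrects.
- Baseline VAS is not a stratification factor, so only chance balances it between arms. Any imbalance moves the change-score estimate.
- If gender or leg pain predicts outcome, ignoring them leaves explainable variance in the error term.

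At stake are the width of the interval for the VAS difference and the stability of the reported estimate. Separately, SAP 5.6 leaves the covariates of the repeated-measures models open in an open-label trial, and naming them in advance removes an analyst's choice.

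**Working it through.** **1. The plan's own figure.** Inputs from SAP section 4: 60% against 30%, 50 per arm, two-sided 0.05.

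- Pooled rate 0.45; null SE = √(2 × 0.45 × 0.55 / 50) = 0.0995
- Alternative SE = √(0.24/50 + 0.21/50) = 0.0949
- Power = Φ[(0.30 − 1.96 × 0.0995) / 0.0949] = Φ(1.107) = 86.6%

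The stated figure, above 85%, reproduces.

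**2. Variance of the two VAS analyses.** Let s_b and s_f be the baseline and 6-month SDs and r their correlation. The documents give none of these, so all are assumed.

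- Change score: s_b² + s_f² − 2·r·s_b·s_f
- ANCOVA on baseline: s_f²·(1 − r²)
- Saving: (s_b − r·s_f)², which is zero when r = s_b/s_f

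Entry requires VAS of at least 6.0 on a 10 cm scale, so baseline spread is likely to be narrower than follow-up spread. For s_b = 1.0, s_f = 2.5 and 50 per arm, the t-test half-width is 1.984 × √(variance × 2/50). The last column is simulated for the full ANCOVA (arm, baseline VAS, gender, leg pain), with gender and leg pain not prognostic.

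| r | Variance, change | Variance, ANCOVA | Saving | t-test half-width, cm | Simulated change in width |
|---|---|---|---|---|---|
| 0.1 | 6.75 | 6.19 | 8.3% | 1.03 | −3.1% |
| 0.2 | 6.25 | 6.00 | 4.0% | 0.99 | −1.0% |
| 0.3 | 5.75 | 5.69 | 1.1% | 0.95 | +0.6% |
| 0.4 | 5.25 | 5.25 | 0.0% | 0.91 | +1.1% |
| 0.5 | 4.75 | 4.69 | 1.3% | 0.86 | +0.4% |

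The simulated gain falls short of the formula because three extra covariates cost about 1% of width at this sample size.

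**3. Wider grid.** Baseline SD 0.8, 1.0, 1.15; follow-up SD 2.0, 2.5, 3.0; r from 0.1 to 0.5: 45 combinations. Each was simulated with 100 subjects, 15 sites, blocks of 4 within site × gender × leg pain, 50% women and 70% with leg pain (both shares assumed).

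- Gender and leg pain not prognostic: from 8.7% narrower to 1.1% wider, mean 0.8% narrower; wider in 22 of 45. A formula approximation that ignores the stratified allocation puts the worst case at 1.6% wider, hence about 1–2%.
- Gender and leg pain explaining 10% of the variance left after baseline VAS: 4.1% to 13.4% narrower, mean 5.9%.

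The baseline SD of 1.15 is that of a uniform distribution on 6–10 (4/√12). It is an assumed value, not a ceiling; the largest SD possible on that range is 2.0. With s_b = 1.3, s_f = 2.0 and r = 0.1, the variance saving is 1.1²/5.17 = 23%, about 12% of width before the covariate cost. The ranges above are therefore not bounds.

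**4. Chance imbalance.** With s_b = 1.0, the baseline difference between arms has SE 1.0 × √(2/50) = 0.20 cm. A 2-SE imbalance (0.40 cm) shifts the change-score estimate, relative to ANCOVA, by 0.40 × (1 − 2.5r): 0.30 cm at r = 0.1, 0.10 cm at 0.3 and zero at 0.4.

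**5. Validity.** If gender, leg pain and site together explain 10% or 20% of the variance, the t-test's true size with 100 subjects is 4.4% or 4.0%: slightly conservative, never inflated in these settings.

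**The case against.** The strongest reply is that nothing is broken. The t-test is valid, baseline VAS is already subtracted, gender and leg pain are balanced by design at randomization, and the base-case gain is about nil: with non-prognostic strata, ANCOVA gives a wider interval in almost half of the combinations. By the formula approximation, the half-width moves by less than 0.03 cm in 41 of the 45. The consistent gains appear only if prognostic strength is assumed, and no passage supplies it. The simulations also use 100 complete cases, whereas about 150 are to be randomized and multiple imputation takes over when data are missing. All of this stands, and it is why the point is optional.

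One part does not carry the weight put on it. Having gender and baseline VAS in the imputation model helps fill in missing values; the comparison made afterwards is still unadjusted.

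A reader might infer stronger claims that the documents do not support:

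- *That the planned tests are invalid or the trial underpowered.* Steps 1 and 5 show otherwise.
- *That the success criterion is at risk.* Protocol B.8.2 ties it to the primary test, which this point leaves alone.
- *That the responder test should be adjusted too.* In simulation this changed power by about −1 to +4 points, but the adjusted test had a size of 5.4% to 6.0%, so the upper end is flattering. No variance correction has been shown to mend that.
- *That SAP 5.6 excludes covariates.* It is silent, which is missing detail and not a stated exclusion.
- *That site should be added.* With up to 15 × 2 × 2 = 60 cells, leaving it out is reasonable.

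**Conclusion.** The omission is certain; the benefit of repairing it is not. The 6-month VAS comparison makes no use of gender or leg pain and uses baseline VAS only by subtraction. Adjusting for all three would change the confidence interval from about 1–2% wider to about 9% narrower if gender and leg pain are not prognostic, and make it about 4–13% narrower if they explain 10% of residual variance. These figures rest on assumed SDs, correlations, prognostic strength and covariate mix, with 100 complete cases. Only the secondary VAS estimate is affected. This is a low-priority improvement, not an error in the plan.

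**What to change.** Before the analysis, add to SAP 5.7.2 an ANCOVA of 6-month back VAS on arm, baseline back VAS, gender and leg pain. If data are missing, fit it in each imputed dataset and combine the results as in SAP 5.7.2.1. Keep the 0.65 cm margin: with baseline VAS in the model, the arm coefficient is the same whether the outcome is 6-month VAS or change. Name the same covariates in the SAP 5.6 repeated-measures model for mean change. Leave site out of both, keep the Pearson chi-square as the primary test, and do not add an adjusted responder analysis unless a named variance method is first shown to hold its size.

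As a supportive analysis this needs SAP text only. Replacing the t-test would need a formal amendment with ethics committee approval, because Protocol B.9.2.2 names the t-test and E.6 governs changes; that is worth doing only if the protocol is being amended anyway.

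The cost is a little programming and no new data: gender and leg pain are needed to randomize, and baseline VAS is the entry score (Protocol B.6.2). The statistical price is up to about 1–2% of interval width if the covariates turn out not to be prognostic.

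Adding leg pain to the imputation list is a related choice but not part of this fix. No calculation here sizes its effect, and those models are fitted separately by arm under a rule that "Explorations to omit predictors may be conducted if the primary effectiveness multiple imputation models will not converge".

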### B.7.3. Primary Endpoint

Pain rating on the 10 cm Visual Analog Scale (VAS) is considered the primary outcome measure. VAS is the most widely used outcome measure in assessing pain due to its documented reliability and validity, ease in administration, and minimal training requirements for the administrator.

- ***Individual Responder:*** A decrease in back pain VAS by at least 50% at 6 months Post-Permanent Device Activation (Test group) or 6 months post-randomization (Control group) as compared with Baseline.

**Overall Study Success:** The percentage of Individual Responders in the test group is shown to be statistically superior to the percentage of Individual Responders in the control group.

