#### B.7.4. Secondary Endpoints

The following secondary endpoints will be evaluated:

- Comparison of the percentage of Individual Responders between the test and control groups in a statistical test of superiority over time. In addition, data will be summarized at the individual time points at 1 month, 3 months, 6 months, 9 months, 12 months, 18 months, and 24 months.
- Comparison of change from Baseline in VAS back pain score between test and control in statistical tests of non-inferiority and superiority at 1 month, 3 months, 6 months, 9 months, 12 months, 18 months, and 24 months . This is calculated as: Change from Baseline in Back Pain VAS = Follow-up Visit Pain VAS – Baseline Pain VAS. A negative result reflects a decrease in the Pain VAS, while a positive result reflects an increase in Pain VAS.

Analysis of results through 6 months will be based on the mITT population. Sensitivity analysis of both secondary endpoints will also be performed to assess the impact of crossover.

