### B.9.2.2 Secondary Analyses

The following *secondary endpoints* will be evaluated:

- If the primary efficacy endpoint in the test group is found to be superior to that in the control group, then a secondary endpoint will evaluate whether the proportion of subjects who achieve a 50% improvement in their back pain VAS score at 1, 3, 9, 12, 18 or 24 months in the test group is superior to that in the control group. A superiority test based on the difference in proportions will be performed based on the following null hypothesis, with a two-sided p-value of 0.05 or less considered evidence of statistical significance.

$H_0$ : The proportion of subjects (P) who achieve a 50% improvement in their back pain VAS score at 1, 3, 9, 12, 18, or 24 months in the Test group is less than or equal to that in the Control group.

$$P_{\text{Test}} = P_{\text{Control}}$$

$H_1$ : The proportion of subjects (P) who achieve a 50% improvement in their back pain VAS score at 3 months in the Test group is greater than that in the Control group.

$$P_{\text{Test}} \neq P_{\text{Control}}$$

- Change in mean VAS will be evaluated with two-sample t-test of non-inferiority in means with a 0.65 cm non-inferiority margin at 6 months.

$H_0$ : The change (C) in subject's VAS pain intensity score relative to baseline at the Primary Efficacy Assessment in the Test group is worse than that of subjects in the Control group by more than 0.65 cm.

$$C_{\text{Test}} \geq C_{\text{Control}} + 0.65 \text{ cm}$$

$H_1$ : The change (C) in subject's VAS pain intensity score relative to baseline at the Primary Efficacy Assessment in the Test group is no more than 0.65 cm worse than the mean change from baseline in the control group.

$$C_{\text{Test}} < C_{\text{Control}} + 0.65 \text{ cm}$$

The non-inferiority margin of 0.65 cm was selected based on a previous study of a similar therapy against traditional SCS. In that study, the experimental therapy showed a 4.9 point improvement while traditional SCS showed a 3.6 point improvement for a difference of 1.3 points. Taking 50% of this treatment effect yields the margin of 0.65 cm. If the null hypothesis is successfully rejected for the non-inferiority test, a test for superiority of treatment to control will be performed based on a two-sided 0.05 alpha level.

The following secondary endpoints do not have an associated hypothesis, and no significance level will be assigned to statistical tests that may be performed.

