5.1.3 Statistical Significance

Unless otherwise specified, hypothesis testing will be performed at the two-sided 0.05 significance level. P-values will be rounded to three decimal places. If a p-value is less than 0.001 it will be reported as "<0.001". If a p-value is greater than 0.999, it will be reported as ">0.999".

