The following secondary endpoints do not have an associated hypothesis, and no significance level will be assigned to statistical tests that may be performed.

- Comparison of Back Pain Treatment Success (responder rate), measured as subjects with at least a 50% reduction in Back Pain VAS, between test and control
- Comparison of mean change from Baseline in Back Pain VAS, between test and control.

Repeated measures models will be used to produce estimates for these two secondary endpoints, with graphical presentation of the responder rates and mean changes from baseline.

Analysis of results through 6 months will be based on the mITT population. For time points after 6 months where crossover is allowed, crossover subjects will be counted as failures (i.e. non-responders) for endpoints defined in terms of responders, carrying forward the baseline (pre-treatment). Sensitivity

Statistical Analysis Plan		Page 12 of 14
Sponsor SGX International	Study EU RCT DTM SCS vs. CMM	Version 3.0

analysis of both secondary endpoints will also be performed to where crossover subjects are censored at the point of crossover.

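### The 0.65 cm non-inferiority margin is taken from a comparison of two SCS therapies but applied against CMM, where nothing in the plan justifies it

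*SAP*

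**What the plan says.** SAP 5.7.2 and Protocol B.9.2.2 set the test in the same terms: "Change in mean VAS will be evaluated with two-sample t-test of non-inferiority in means with a 0.65 cm non-inferiority margin at 6 months". The null hypothesis is that the test group's mean change is worse than control's by at least 0.65 cm. If it is rejected, a superiority test at two-sided 0.05 follows.

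Both documents give the same source for the margin: "The non-inferiority margin of 0.65 cm was selected based on a previous study of a similar therapy against traditional" SCS. Improvements of 4.9 and 3.6 points are cited, a difference of 1.3, and then: "Taking 50% of this treatment effect yields the margin of 0.65 cm". The Protocol's reference list identifies the source as a trial of high-frequency against traditional low-frequency SCS.

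Other passages fix the status of the test:

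- The responder tests at the other visits in SAP 5.7.2 are conditional: "If the primary efficacy endpoint in the test group is found to be superior to that in the control group". The non-inferiority test carries no such condition.
- SAP 5.7.2 then separates off the repeated-measures comparisons: "The following secondary endpoints do not have an associated hypothesis, and no significance level will be assigned to statistical tests that may be performed". The non-inferiority test stands before that line, with its own hypotheses.
- Overall success in Protocol B.7.3 is a superiority criterion: "The percentage of Individual Responders in the test group is shown to be statistically superior" to that in control. The Definition of Success section (the second one numbered B.8.2) adds no success criterion for secondary endpoints.
- Protocol B.7.4 asks, for mean change, for "statistical tests of non-inferiority and superiority at 1 month, 3 months, 6 months, 9 months, 12 months, 18 months, and 24 months". Protocol B.9.2.2 and SAP 5.7.2 set the non-inferiority test at 6 months only.

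**The concern.** A non-inferiority margin has meaning only relative to its comparator. It should either preserve a stated share of the control's known effect or represent a loss against that control which has been argued to be tolerable. Half of the advantage of one stimulation therapy over another does neither when the control is CMM without stimulation.

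The design makes the gap more awkward. The test arm receives CMM plus an implanted system, and the sample size basis (Protocol B.5.5.1) and success rule are both superiority. Rejecting the null hypothesis does validly exclude a deficit of 0.65 cm against CMM. However, the plan does not say why that is worth knowing, or why 0.65 cm is the right threshold.

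What is at stake is reporting. Because the test does not depend on the primary endpoint, non-inferiority to CMM could be presented as a positive hypothesis-tested result after the primary fails, even if the implant adds no pain relief. The conflict between one visit and seven also leaves open how many such claims the protocol allows.

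**Working it through.** **1. The plan's own figure.** 4.9 − 3.6 = 1.3 and 0.5 × 1.3 = 0.65 cm. The arithmetic reproduces; the mismatch is in the comparator.

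| | Source of the margin | This trial |
|---|---|---|
| Test | high-frequency SCS | DTM SCS + CMM |
| Control | traditional low-frequency SCS | CMM alone |

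The nearest figure to a CMM effect in either document is the 30% control responder rate assumed in Protocol B.5.5.1 and SAP 4. That is a planning rate for a dichotomised endpoint. It is not a mean VAS change under CMM, an effect of CMM over no treatment, or a tolerable loss.

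**2. Inputs for the illustration.**

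- Margin: 0.65 cm.
- Level: one-sided 0.025, taken from the default that "hypothesis testing will be performed at the two-sided 0.05 significance level" (SAP 5.1.3), since no separate level is given for this test.
- Sample size: 50 per arm, the required number, and 75 per arm (150 randomized ÷ 2, before attrition), which is an upper bound.
- SD of change: not in the documents. I assume 2.0, 2.5 and 3.0 cm.
- True difference: zero.

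**3. Formulas.** The difference is test minus control in change from baseline, so a negative value favours the implant.

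- SE = SD × √(2/n)
- P(non-inferiority declared | no difference) = Φ(0.65/SE − 1.96)
- Observed difference needed to pass: below 0.65 − 1.96 × SE

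For SD 2.5 and n = 50: SE = 2.5 × √0.04 = 0.500, Φ(1.30 − 1.96) = 0.255 (0.2546), and 0.65 − 0.98 = −0.33.

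| n per arm | SD (cm) | SE | P, normal | P, exact noncentral t | Observed difference needed (cm) |
|---|---|---|---|---|---|
| 50 | 2.0 | 0.400 | 0.369 | 0.363 | −0.13 |
| 50 | 2.5 | 0.500 | 0.255 | 0.251 | −0.33 |
| 50 | 3.0 | 0.600 | 0.190 | 0.188 | −0.53 |
| 75 | 2.0 | 0.327 | 0.512 | 0.507 | +0.01 |
| 75 | 2.5 | 0.408 | 0.357 | 0.353 | −0.15 |
| 75 | 3.0 | 0.490 | 0.263 | 0.261 | −0.31 |

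A favourable superiority result with no true difference occurs in 2.5% of trials. These non-inferiority declarations are not type I errors, since a true difference of zero lies inside the margin. They show how often the claim would be available when the implant adds nothing.

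**4. Overlap with a failed primary.** If the arms do not differ at all, the primary favours the test arm in nominally 2.5% of trials. At SD 2.5 and 50 per arm, non-inferiority would therefore be declared without a favourable primary in at least 0.255 − 0.025 = 0.230, or 23%, of trials.

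**5. Does the non-inferiority step protect the superiority test?** A 95% confidence interval wholly below 0 is also wholly below +0.65, so any favourable superiority result passes non-inferiority automatically. In a simulation of 50,000 trials per sample size (SD 2.5, no true difference), non-inferiority was declared in 25.2% (n = 50) and 35.2% (n = 75) and favourable superiority in 2.6% and 2.5%. Superiority without non-inferiority never occurred.

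**6. Primary power, for the cost of an optional gate.** At 60% vs 30% with 50 per arm, the null SE is √(2 × 0.45 × 0.55/50) = 0.0995 and the alternative SE is √(0.6 × 0.4/50 + 0.3 × 0.7/50) = 0.0949. Power is Φ((0.30 − 1.96 × 0.0995)/0.0949) = 0.866; the exact binomial value is 0.876. Both agree with the stated figure of more than 85%.

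**The case against.** The strongest reply has four parts.

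- **The endpoint is secondary.** Study success rests on the primary alone, and testing non-inferiority and then superiority in fixed order does not inflate type I error. Both points are right. They limit the weight of the issue, but they do not supply a rationale for the margin.
- **Non-inferiority could still be informative.** The secondary objectives in Protocol B.2 are to document effectiveness against CMM and are not confined to superiority. Protocol B.6.19 allows the investigator to reduce pain medication in the SCS arm after activation, so similar pain scores might have some meaning. That argument could have been made, but neither document offers it as the reason for 0.65 cm or for any other margin.
- **Passing nearly always needs a favourable observed mean.** This is true: in five of the six scenarios the observed difference must favour the implant, by 0.13 to 0.53 cm. An observed lean of that size still does not establish a benefit, and the formal claim would be of non-inferiority against an unjustified threshold.
- **Misleading reporting is conjecture, and the percentages rest on assumed SDs.** No document plans such a claim, and the figures are illustrative. It remains the case that the plan pre-specifies the hypothesis, does not condition it on the primary, and so makes the claim available.

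The B.7.4 discrepancy is a separate wording matter. It needs reconciling, but it adds nothing to the case about the margin.

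**Conclusion.** The concern holds. The margin's arithmetic is right, but its source contrast is SCS against SCS, and neither document justifies it for SCS plus CMM against CMM alone. Rejecting the null hypothesis would exclude a 0.65 cm deficit and nothing more.

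The practical size is that, at 50 per arm, roughly one trial in five to more than one in three would declare non-inferiority with an implant that adds no pain relief. At 75 per arm the figure is at most 26% to 51%. This assumes an SD of change of 2.0 to 3.0 cm, which the documents do not give, and a one-sided 0.025 level inferred from SAP 5.1.3. The mismatch itself depends on neither assumption.

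The plan should be changed on this point. The primary analysis and the success decision are not affected.

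**What to change.** Delete the non-inferiority hypothesis and margin from Protocol B.7.4, Protocol B.9.2.2 and SAP 5.7.2, and put in their place:

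> The difference in mean change from baseline in back pain VAS at 6 months (test minus control) will be tested for superiority at two-sided 0.05.

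Align Protocol B.7.4 with B.9.2.2 so that 6 months is the only hypothesis-tested visit for mean change. Keeping non-inferiority would require a margin justified against CMM, and the documents contain no figure from which to derive one.

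Making the new test conditional on the primary, as the responder tests are, is optional. The price is that it could then succeed only when the primary does, which has about 87% probability under the planning assumptions. Adding that condition while keeping the margin would close the failed-primary route but leave the threshold unjustified.

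The cost is a formal protocol amendment with sponsor, ethics committee and investigator approval (Protocol E.6) and a SAP revision. No patients or visits are added, and no favourable superiority finding is lost.
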